## PROTOCOL

Neurosteroids as Novel Therapeutic Agents for PTSD in OEF/OIF/OND Veterans  
PI: [name], PhD

### Purpose

This is a parallel-group, double-blind, placebo (PBO)-controlled, randomized Phase 2 pilot study using adjunctive dehydroxyepiandrosterone [DHEA (400 mg)] will be evaluated to establish Proof of Concept (POC) for this agent in Veterans with PTSD.

Our first objective is POC target engagement to evaluate a one-time adjunctive oral dose of DHEA (400 mg) relative to PBO on the neuronal circuitry of fear-anxiety-emotion connectivity. This will be achieved by comparing pre- to post-treatment changes in amygdala-hippocampal functional connectivity to DHEA and PBO during fMRI activation. We hypothesize that compared with PBO, DHEA will increase task-associated fMRI functional connectivity between the amygdala and hippocampus (primary outcome).

Our second objective is to determine if an 8-week treatment with adjunctive DHEA is superior to PBO in reducing symptoms of PTSD (CAPS-5) and depression (BDI) in OEF/OIF/OND Veterans, and enhancing resilience (CD-RISC). We hypothesize that 400mg DHEA will result in reduced PTSD and depression symptom severity relative to PBO, as determined by a pre- to post-treatment decrease in CAPS-5 and BDI scores, respectively, with enhancement in resilience scores using the CD-RISC at 6-weeks.

Our third objective is to evaluate the impact of DHEA relative to PBO on serum neurosteroid levels in OEF/OIF/OND Veterans with PTSD. We hypothesize that DHEA will result in a statistically-significant increase in serum neurosteroid levels (DHEA, DHEAS, androsterone) relative to PBO, as determined by pre- to post-treatment reductions in PTSD symptoms severity. This association will be evaluated by correlating neurosteroid levels with PTSD, depression, and resilience scores over 6 weeks of treatment.

Our exploratory objective is to determine preliminary evidence for an association of fMRI and myelin integrity measures of fear-anxiety-emotion circuits with serum neurosteroid levels and treatment response to DHEA. Changes in myelin integrity following DHEA treatment will be evaluated using novel susceptibility diffusion imaging [STI]), as DHEA impacts myelination in preclinical rodent models. We will also determine if serum neurosteroid levels are correlated with myelin integrity on STI. We hypothesize that fMRI and myelin integrity of fear-anxiety circuits will correlate with serum neurosteroids and treatment response.

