### Design

This is a parallel-group, double-blind, placebo (PBO)-controlled, randomized Phase 2 pilot study using adjunctive dehydroxyepiandrosterone [DHEA (400 mg)] will be evaluated to establish Proof of Concept (POC) for this agent in OEF/OIF/OND Veterans with PTSD.

Aim 1. To determine the effects of an acute oral administration of adjunctive DHEA (400 mg) on neuroimaging measures of functional connectivity. We will conduct a parallel-group, double-blind, placebo (PBO)-controlled, randomized Phase 2 pilot study with one-time oral DHEA 400 mg in target engagement. To establish POC, we seek to determine if DHEA is superior to PBO in target engagement of neural circuits related to fear-anxiety-emotion regulation using the shifted-attention emotion appraisal (SEAT) paradigm (see below). Following a two-week placebo lead-in period (all participants), subjects will be randomized to receive a one-time oral dose of adjunctive DHEA (400mg) or PBO. Neuroimaging will occur 2 hours following drug administration for peak level effects on target engagement of fear-anxiety emotion circuit connectivity, as previously conducted by Sripada, [name], [name] et al.).

Primary Outcome Measure The primary outcome measure will be functional connectivity between amygdala-hippocampus assessed using fMRI based SEAT Paradigm as a target engagement endpoint. The fMRI based SEAT Paradigm has been previously validated to an acute administration of DHEA (400 mg) in healthy volunteers by members of my career development team, Drs. [name] and [name] (Sripada et al., 2013).

Aim 2. To evaluate a sustained 6-week adjunctive DHEA treatment compared to PBO on PTSD symptoms severity (CAPS-5), co-occurring depression (BDI), and other secondary outcome measures such as resilience (CD-RISC). Following randomization to acute DHEA administration or PBO the subject will continue to receive study drug for 6 weeks (for DHEA, fixed escalating doses: 100 mg per day in divided doses x 1 week, followed by 200 mg per day in divided doses x 1 week, followed by 400 mg per day in divided doses x 4 weeks).

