## PROTOCOL

Neurosteroids as Novel Therapeutic Agents for PTSD in OEF/OIF/OND Veterans  
PI: [name], PhD

and fMRI. We estimate that approximately 80% of all participants enrolling in the proposed randomized controlled trial will also receive neuroimaging to an acute administration of DHEA or PBO placebo and post-treatment with DHEA or PBO. We thus anticipate that approximately 32 or more participants will undergo neuroimaging to an acute treatment with DHEA or PBO and at study completion (a minimum of approximately 16 participants per group in this pilot POC study). Susceptibility tensor imaging is a new methodology created by our collaborator at Duke, [name].

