## PROTOCOL

Neurosteroids as Novel Therapeutic Agents for PTSD in OEF/OIF/OND Veterans

PI: [name], PhD

whether buildings are indoors or outdoors; or (3) 'Like/Dislike': whether the face is liked or disliked. This task probes emotion regulation: (1) implicit emotional processing, (2) attentional modulation of emotion, and (3) modulation of emotion by appraisal. The 'Gender' condition probes implicit emotional processing, as attention is focused on an emotional face while identifying its gender, and it is established that negative emotional faces induce negative emotions. The 'Inside/Outside' condition engages attentional modulation of emotion as in focusing attention on the building components superimposed on the emotional face. Attention modulation is recognized as a core component of emotion regulation. The 'Like/Dislike' condition engages cognitive appraisal of one's emotional/evaluative state and engaging appraisal increases activation of dorsal medial prefrontal cortex ([name] et al, 2000; Phan et al, 2004). Behavioral studies of emotional appraisal find that this strategy lowers distress (Lieberman et al, 2011). The ability of DHEA to impact functional connectivity between the amygdala and hippocampus in healthy volunteers undergoing the SEAT paradigm will be evaluated in Veterans with PTSD to an acute target engagement dose of DHEA (400 mg) and following a sustained 6-week treatment.

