### Study Interventions

We will conduct a parallel-group, double-blind, placebo (PBO)-controlled, randomized Phase 2 pilot study with 400mg DHEA to test whether we can establish proof of concept (POC) for this agent. 40 OEF/OIF/OND Veterans with PTSD will be randomized to receive a one-time oral adjunctive treatment with DHEA or PBO in the fMRI paradigm (same day). Participants will then continue to receive a 6-week sustained treatment of DHEA or PBO. To establish POC, we seek to determine whether DHEA is superior to

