## PROTOCOL

Neurosteroids as Novel Therapeutic Agents for PTSD in OEF/OIF/OND Veterans  
PI: [name], PhD

PBO on neural circuits related to fear-anxiety-emotional regulation. We will determine potential fear-anxiety circuit target engagement following one-time oral adjunctive dose of DHEA (400 mg) using a same-day fMRI paradigm (the SEAT procedure, see below) to assess derived functional connectivity measures between the amygdala and the hippocampus as compared to PBO (primary outcome). Further, we will also determine if fMRI and serum neurosteroids (DHEA, DHEAS, androsterone, and/or other neurosteroids) may be candidate biomarkers of PTSD symptoms (CAPS-5) that predict therapeutic response to a DHEA intervention (secondary outcomes). The proposed set of studies will enable us to investigate these neurosteroids as novel pharmacological interventions for PTSD, and to identify biomarkers of therapeutic response in PTSD. Finally, as an exploratory goal, the current study will determine if treatment with DHEA impacts myelin integrity (as assessed by STI), and if peripheral neurosteroid levels are potentially associated with myelin content, other neuroimaging parameters, or therapeutic response.

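### The analysis labelled primary does not test the named primary outcome (amygdala-hippocampal connectivity), and objective 1's pre- to post-treatment change has no described pre-dose scan

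*Combined protocol and SAP*

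**What the plan says.** **Primary outcome.** The hypothesis under Purpose is that "compared with PBO, DHEA will increase task-associated fMRI functional connectivity between the amygdala and hippocampus (primary outcome". Design states: "The primary outcome measure will be functional connectivity between amygdala-hippocampus assessed using fMRI based SEAT Paradigm as a target engagement endpoint". Study Interventions repeats this for the one-time dose, "to assess derived functional connectivity measures between the amygdala and the hippocampus as compared to PBO (primary outcome".

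**How objective 1 is to be met.** Purpose says by "comparing pre- to post-treatment changes in amygdala-hippocampal functional connectivity to DHEA and PBO during fMRI activation".

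**When imaging takes place.** Under Aim 1, randomisation and the one-time dose follow the two-week placebo lead-in, and "Neuroimaging will occur 2 hours following drug administration for peak level effects on target engagement". The Exploratory Aim says participants "will undergo neuroimaging to an acute treatment with DHEA or PBO and at study completion". The SEAT description gives the same two occasions: "to an acute target engagement dose of DHEA (400 mg) and following a sustained 6-week treatment". The Schedule of Events marks MRI at Weeks 2 and 8 only, and the payments section counts two MRIs.

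**Analysis.** Data Analysis and Statistical Considerations first lists a whole-brain BOLD comparison that includes pre- versus post-treatment, without saying which scan is the pre-treatment one. It then bases the primary outcome analyses on activation maps, reaction time and accuracy, in a 2 (drug) × 3 (face) × 3 (condition) ANOVA. The same paragraph ends with a PPI analysis. One sentence takes its time series from significant clusters of group difference. The next takes a seed from the anatomical right amygdala in every subject. The regressor of interest is seed by experimental condition.

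**The concern.** The proof-of-concept claim rests on one endpoint. If the analysis section is followed literally, the result reported as primary would concern activation or task behaviour, which are different outcomes from connectivity. The connectivity result would come from a step with no stated target region, arm comparison or scan.

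The wording of the objective adds a second difficulty. An analyst told to compare pre- to post-treatment changes, and holding scans from Weeks 2 and 8, could take Week 2 as the pre-treatment scan. By the plan's own timing, that scan follows the randomised dose.

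**Working it through.** **Step 1. Count the scans.** Inputs are the MRI row of the Schedule of Events (Weeks 2 and 8) and the payments section ($75 per visit, $100 per MRI, 5 visits, 2 MRIs, total $575).

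- 5 × 75 + 2 × 100 = 575, which reproduces the stated total.
- A third paid MRI would give 5 × 75 + 3 × 100 = 675, which is not what is stated.
- The Week 2 scan is 2 hours after the randomised dose, and the Week 8 scan follows sustained treatment. So 0 of the 2 scheduled MRIs is described as preceding the randomised dose.

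**Step 2. What each contrast estimates.** Let the placebo means be m0 (a hypothetical pre-dose scan), m2 (Week 2) and m8 (Week 8). Let A be the acute drug effect and S the sustained effect. The DHEA means are then m0, m2 + A and m8 + S.

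- Arms at Week 2: (m2 + A) − m2 = A.
- Change from a pre-dose scan: [(m2 + A) − m0] − [m2 − m0] = A.
- Week 8 minus Week 2: [(m8 + S) − (m2 + A)] − [m8 − m2] = S − A.

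The first two contrasts target the same quantity because randomisation gives both arms the same expected m0. They differ only in precision. The third is zero whenever S = A, however large A is, and equals −A if the effect does not persist. It cannot stand in for the acute effect.

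**Step 3. Set outcome against analysis.**

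| | Outcome statements | Analysis labelled primary | PPI text |
|---|---|---|---|
| Measure | Amygdala-hippocampal connectivity | Activation, reaction time, accuracy | Seed-by-condition interaction |
| Region | Amygdala and hippocampus, side not given | ROIs not named | Right amygdala seed, no target named |
| Comparison | DHEA versus placebo | Drug factor in the ANOVA | No between-arm test stated |
| Scan | 2 hours after the one-time dose (Design) | Not stated; no time or baseline term | Not stated |
| Status | Primary | Primary | Not stated separately |

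None of the three outcome types in the middle column is connectivity, and the hippocampus is not named anywhere in the analysis section. The two PPI sentences also pull apart. Read by the cluster sentence, connectivity is examined only where activation differs between arms. Read by the anatomical-seed sentence, it is examined regardless. The text does not say which governs.

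**The case against.** The best defence is that this is one combined document and should be read as a whole. Design fixes the measure, the placebo comparator and the timing of 2 hours after the randomised dose; Study Interventions repeats the measure, the comparator and the one-time dose. The PPI stands in the same paragraph as the primary outcome analyses and has a named method, seed and regressor. Much of this stands, and it rules out three stronger readings.

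- A reader might infer that the analysis section contains no connectivity method. It does: the PPI. What it lacks is the hippocampal target, the DHEA-versus-placebo test of the PPI estimate, its status and the scan.
- A reader might infer that scan, measure and contrast are all open to choice after the data are seen. Design and Study Interventions constrain the measure, comparator and timing. What stays open is mainly the SEAT contrast, the hippocampal region and side, whether the test is on an ROI mean or voxelwise, and which analysis carries the primary claim.
- A reader might infer that the stated change is impossible to form. The Schedule of Events marks visits, not scanner runs, and participants "will be randomized to receive a one-time oral adjunctive treatment with DHEA or PBO in the fMRI paradigm (same day", so a pre-dose run within the Week 2 session is not excluded. But no section describes one, and the stated timing points against it. The supportable statement is that no pre-dose scan is described.

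The defence does not remove the conflict between a primary outcome of connectivity and a primary analysis of activation and behaviour. Reading the sections together exposes that conflict.

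**Conclusion.** The concern holds as an inconsistency and incomplete specification in two parts of unequal weight.

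1. **More serious.** The analysis labelled primary is not an analysis of the named primary outcome, and the PPI text does not supply the missing between-arm test. This affects the trial's single primary outcome and should be corrected before unblinding.
2. **Less serious.** The change wording in objective 1, and the unlabelled pre/post contrast in the fMRI analysis text, do not match the imaging described. The hypothesis sentence and the Design outcome already fit a between-arm comparison at Week 2, which is valid by randomisation.

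The size is a count: 0 of 3 outcome types in the primary analysis is connectivity, and 0 of 2 scheduled MRIs is described as pre-dose. The documents give no effect size, SD or within-person correlation for connectivity, so no loss of power can be derived from them. Counting ANOVA effects would not measure the problem either, since correction for multiple comparisons is specified. The conclusion assumes that the imaging described is all the imaging planned. It does not mean that the trial is unable to test its primary hypothesis.

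**What to change.** 1. **Data Analysis, primary outcome paragraph.** Make the primary analysis the DHEA-versus-placebo comparison of amygdala-hippocampal PPI connectivity on the Week 2 scan. Use an anatomical amygdala seed (the text already uses the right) and an anatomically defined hippocampal target, and run it whatever the activation result. Fix the SEAT contrast, the hippocampal side and the choice of ROI-mean or voxelwise test before unblinding. Treat activation, reaction time and accuracy as supporting.
2. **Purpose, first objective.** Replace the pre- to post-treatment wording with the between-arm comparison on the Week 2 post-dose scan, matching Design and Study Interventions. If a pre-dose run was intended, state it instead in Design and the Schedule of Events, and add a baseline term to the primary analysis.
3. **Data Analysis, fMRI paragraph.** State the between-arm contrasts at Week 2 and Week 8 separately. Label any Week 8 minus Week 2 contrast as sustained minus acute effect.

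**Cost.** The preferred route changes wording only. Activation and behavioural results can no longer be claimed as primary. A post-only comparison also forgoes baseline precision: adjusting for a pre-dose scan with within-person correlation r would multiply the variance of the arm comparison by about 1 − r². That is 0.91, 0.75 or 0.51 at r = 0.3, 0.5 or 0.7, values assumed here because the documents give none. If the alternative meant a separately paid MRI, it would add $100 per participant (32 × 100 = $3,200 to 40 × 100 = $4,000), plus scanner time and burden.

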### Background and Significance

*Background:* Posttraumatic stress disorder (PTSD) is extremely common among Operation Enduring Freedom/Operation Iraqi Freedom/Operation New Dawn (OEF/OIF/OND) Veterans, impacting approximately 20% of OEF/OIF/OND Veterans enrolled in VA healthcare. Pharmacological management of PTSD is unfortunately frequently suboptimal, and many OEF/OIF/OND Veterans experience persistent and

## PROTOCOL

Neurosteroids as Novel Therapeutic Agents for PTSD in OEF/OIF/OND Veterans  
PI: [name], PhD

unalleviated symptoms. Currently there are *only two* FDA-approved pharmacological treatments for PTSD (sertraline and paroxetine, each approved ~15 years ago). **There is thus an acute and urgent need for the development of new pharmacological treatments for PTSD that are effective and well-tolerated.** Neurosteroids are endogenous molecules that are enriched in human brain, and many neurosteroids exhibit anxiolytic-like actions and modulate the HPA axis. In addition, neurosteroids such as dehydroepiandrosterone (DHEA) are immediately accessible for translation to clinical trials, as DHEA is available over-the-counter as a dietary supplement in the U.S. Neurosteroid interventions may represent an important new lead for the management of PTSD symptoms in OEF/OIF/OND Veterans. Based on our preliminary data in 660 OEF/OIF/OND male Veterans (indicating DHEAS levels as significantly reduced in PTSD) and rodent data from multiple research groups demonstrating anxiolytic actions of neurosteroids.

Several groups of investigators have reported that serum DHEA and/or DHEAS levels are altered in PTSD (Kanter 2000; Spivak et al., 2000; Sondergaard et al., 2002, and Rasmussen et al., 2004; Yehuda et al., 2006). Possibly contributing to somewhat mixed findings, prior studies contained relatively small numbers of participants with PTSD (the largest study reports findings for 52 participants with PTSD), and few studies controlled for age and smoking in their analysis plans (two critical co-variates). In contrast, our DHEAS findings support the current project include 213 OEF/OIF/OND Veterans with PTSD, controlling for age and smoking (we report DHEAS levels in a total over 660 OEF/OIF/OND Veterans). It has been hypothesized that greater DHEA release following ACTH administration may represent a compensatory response to severe stress (Rasmussen et al 2004). In a small sample of untreated Israeli male combat Veterans with chronic PTSD, higher plasma DHEA and DHEAS levels were observed in comparison to healthy male control subjects without PTSD (Spivak et al., 2000); however, it is unknown if DHEA and/or DHEAS levels were correlated with PTSD symptoms specifically in that investigation. Perhaps even more importantly, serum DHEAS levels are positively associated with resilience in several recent studies (Petros et al., 2013; Radant et al., 2001, Taylor 2013), and a series of innovative investigations in Special Forces also support the concept that DHEAS is associated with enhanced resilience (Morgan et al 2009, 2004). It is thus possible that treatment with DHEA has the potential to increase resilience among OEF/OIF/OND Veterans with PTSD. Although difficult to quantify as a variable that is sensitive to change, initial studies suggest that the Connor-Davidson Resilience Scale (CD-RISC) may be a useful tool to begin to understand the construct of resilience (Davidson et al 2008), as the neurobiological underpinnings of resilience continue to be elucidated (McEwen et al 2015, Russo et al 2012). Recent neuroimaging evidence also supports a possible role for DHEA in the treatment of PTSD. Specifically, efforts in collaboration with investigators at the University of Michigan ([name] and [name]) demonstrate that *one-time DHEA administration (400 mg orally) appears to alter functional connectivity between the amygdala and the hippocampus (Sripada et al 2013, 2014)*, brain regions that are implicated in the pathophysiology of PTSD. *In*

## PROTOCOL

Neurosteroids as Novel Therapeutic Agents for PTSD in OEF/OIF/OND Veterans  
PI: [name], PhD

*addition, peripheral DHEA levels were associated with neuroimaging parameters on fMRI (Sripada et al 2013, 2014).* It is thus possible that characterization of serum neurosteroids during fMRI tasks implicating anxiety behaviors may help clarify the neurobiological mechanisms of the anxiolytic actions of these molecules. DHEA administration in humans (healthy controls) was also associated with greater activity in anxiety regulatory processes and with reductions in negative emotion circuits (Sripada et al., 2013). These fMRI findings following DHEA administration support the possibility that Veterans with PTSD and co-occurring symptoms may benefit from the enhancement of levels of this neurosteroid (Sripada et al., 2014). Resting state brain activity in response to DHEA administration both reduces amygdala and dorsolateral prefrontal cortex connectivity, and shifts the balance between salience and default networks for anxiety reduction (Sripada et al., 2014b). Recently, a fear generalization paradigm in Veterans with PTSD using fMRI indicated that amygdala-thalamus and amygdala-calcarine sulcus connectivity are increased, which may represent neurobiological correlates of triggering PTSD symptoms by threat cues resembling index trauma (Morey et al., 2015). Serum levels of DHEAS in healthy subjects also negatively correlate with fear-potentiated startle (Grillon et al, 2006), an experimental paradigm viewed largely as one with possible relevance to PTSD (Norrholm et al., 2011).

The majority of research in Veterans with PTSD that has focused on white matter assessment has utilized diffusion tensor imaging (DTI). Reductions in fractional anisotropy in cingulum (white matter fibers that project from the amygdala to prefrontal cortex; involved in emotion processing) and other areas near the prefrontal cortex (Kim et al., 2005; 2006; Schuff et al., 2011; Zhang et al., 2011) have been reported in patients with PTSD. Overall, however, DTI studies in PTSD have been somewhat mixed (Daniels et al., 2013 review). Technological limitations of DTI may be contributing to these disparate results among PTSD investigations, as DTI lacks the resolution and sensitivity required for the optimal assessment of white matter microstructure (Cao et al., 2014). As an exploratory aim, we are thus proposing to use a new neuroimaging technology - quantitative susceptibility mapping and susceptibility tensor MRI (QSM/STI), which provides superior resolution and sensitivity to non-invasively assess *in vivo* fiber tract alterations in Veterans with PTSD. This is a promising new technology created by our collaborator at Duke, [name].

**Significance:** This project may lead to a novel new therapeutic for OEF/OIF/OND Veterans with PTSD that is safe, efficacious, inexpensive, and well-tolerated. It could also identify serological and/or neuroimaging biomarkers for therapeutic response, potentially leading to personalized treatments for Veterans with PTSD. There is currently a paucity of safe and effective pharmacological agents for the treatment of PTSD, a disorder that impacts large numbers of OEF/OIF/OND Veterans and is frequently accompanied by co-occurring conditions that include depression and TBI. DHEA may be a promising new therapeutic in PTSD, as it demonstrates anti-anxiety effects in rodent models and fear-anxiety circuit regulation in humans. Based on our

